Key covariates. Patient-level covariates will be identified based on the ICF (Figure 1) and other factors known to assess independence including age, race, ethnicity, marital status, service connection, urban/rural status, NOSOS score from year prior to start date. Site-level covariates to explore will include presence of a Geriatric Research Education and Clinical Center, rural status, and academic affiliation. Data sources will include CDW, Inpatient Evaluation Center (IPEC), Strategic Analytics for Improvement and Learning (SAIL), Geriatrics and Extended Care Data Analysis Center (GECDAC) and the patient medical record.

Sample of Patients. Administrative data and VA/CMS Repository data will be used to construct the primary patient outcome. Analysis will be performed on a sample of Veterans from a 3 or 6-month repeated automated CDW data pull and/or VistaWeb/Joint Legacy Viewer as appropriate. This data pull will occur at a uniform time period (e.g., 2 weeks) of each 3 or 6-month interval for the duration of the 30-month study.

Patient eligibility criteria includes a consult or referral in the past 3 or 6-months from the date of the data pull to the following VA services:

- H/HHA (homemaker home health aide services)
- Home based primary care (HBPC)
- Adult day health care
- Respite care
- Veteran directed care

and meet none of the exclusion criteria:

• Consult or referral to hospice care.

We anticipate that there will be between 15,000 -18,000 total Veteran patients meeting these criteria. We will require sites have a minimum of 50 recent referrals to HCBS (recent is defined as within a 3 or 6-month interval) to be an eligible site.

Sample of Caregivers. Survey data will be used to construct secondary caregiver outcomes.

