To address the impact of the iHI-FIVES program, we will use quantitative methods to examine the effect on patient outcomes. The overall anticipated number of eligible Veteran patients in the iHI-FIVES study will be 15,000-18,000 total patients. The analysis plan of our primary outcome is to examine days at home for the patient over a 6-month interval and will be defined as the total number of days not in the emergency department, nursing home, or inpatient ward. The start date for each patient, or the day of the automated data pull, will be "day 0" for all patients, and the maximum total possible number of days at home will be 180 for all patients. To make this outcome variable easier to deal with analytically, our first step will be to calculate each patients' days not at home by subtracting their number of days at home from 180, converting the "stack" of days at 180 to a "stack" at zero. For days not at home outcome, we anticipate, that it may have an excess of zeros and larger variance than what is to be expected from either a Poisson or Negative Binomial process. Common approaches for analyzing this type of data are the zero-inflated Poisson (ZIP) model and the zero-inflated negative binomial (ZINB) model¹¹⁶ or two-part models.^{117,118} Consequently, we will explore the distribution that best fits this outcome: Poisson, Negative Binomial, ZIP, ZINB, or a semi-continuous distribution such as a two-part gamma.¹¹⁹

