To address if caregivers who participate in iHI-FIVES have higher satisfaction with VA care, lower depressive symptoms, and lower burden, analysis will be conducted at the level of the patient or caregiver utilizing all available data to evaluate iHI-FIVES effectiveness versus control condition on defined count and continuous outcomes. The overall anticipated sample size of eligible caregivers in the iHI-FIVES study will be 320. We will use random effect linear (continuous outcomes), negative binomial (count outcomes), or logistic (dichotomous outcomes) models appropriate for the stepped-wedge design which account for the correlation of patients within the same VAMC.^{34,60} For example with a continuous outcome, I VAMCs, T time points, N individuals per VAMC per time interval, the model is: $Y_{ijk} = \mu + \alpha_i + \beta_j + X_{ij}\theta + e_{ijk}$, where α_i is the random effect for the ith VAMC, β_j is a fixed effect that captures time trends, and X_{ij} is an indicator of the intervention mode for the ith hospital at time j (=0 prior to intervention and =1 post intervention), and θ is the measure of the effect of the intervention. Adjustments for patient characteristics and a random effect for VAMC site may also be added.

Sensitivity analysis. In addition to the primary analysis of the primary and secondary outcomes described above, we will perform an "as treated" analysis focused on the outcomes of Veteran patients from caregivers in the post-implementation period exclusively. This will show us whether there is benefit conferred upon those caregivers/Veterans in the iHI-FIVES program compared to similar caregivers/Veterans not in the program. The treated caregivers will be all caregivers who meaningfully participated in the iHI-FIVES training (e.g., attended at least one class). The comparison caregivers will be selected from the full set of caregivers referred to iHI-FIVES using n:1 matching on key baseline covariates of the patient and caregiver. The rationale for matching on key Veteran baseline covariates is to ensure that we have similar Veteran acuity in both groups, because the training may be differentially effective for caregivers by level of Veteran disability. Candidate matching variables for the patient include:

- Patient age bands
- Patient Jen Frailty Index Score (0-10)
- Patient CAN scores (1 year inpatient use version)
- Dementia status based on ICD9 codes in the past 6 months
- Documentation of incontinence in the past 6 months

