Sample size estimate. For STRIDE, sample size calculations were conducted for patient-level analyses evaluating impact of STRIDE on discharge to skilled nursing facility. The sample size calculation was done based on a complete stepped-wedge design using Hussey and Hughes (2007) method.⁶⁰ The sample size is based on the following assumptions for the discharge to skilled nursing facility outcome: 1) base discharge rate to skilled nursing of approximately 20%; 2) 10% drop in discharge rate after STRIDE, determined as a clinically significant gain in the outcome; 3) intracluster correlations (ICC) ranging from 0.02 to 0.6 for patients within the same hospital; 3) 8 hospital sites with 5 3-month assessment periods; and 4) alpha=0.05, power>80%. A total sample of 2000 patients (~250 per hospital, 50 per 3-month interval) will result in ≥80% power to detect a 10% reduction in discharges to skilled nursing facilities. The anticipated maximum sample is 16,000. For iHI-FIVES, the sample size calculation was done based on a complete stepped-wedge design using Hussey and Hughes (2007) method.⁶⁰ The overall anticipated number of Veteran patients will be 15,000-18,000 with a minimum sample size of 400 subjects (at least 50 per VAMC, 20 per 6-month interval). The power calculation for this sample size is based on the following assumptions for days not at home: 1) 8 is the baseline mean number of days not at home over 6 months; 2) 2-day reduction in days not at home over 6 months; 3) coefficient of variation (CV) ranging from 0.3 to 0.5 for assessments on participants within the same VAMC; 4) 8 VAMCs with five 6-month assessment intervals; and 5) alpha=0.05, power>80%. A minimum sample of 400 Veterans will result in at least 80% power to detect a mean reduction of 2 days not home assuming variance equal to the mean (Poisson distribution).

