Budget impact analyses (BIA). Utilizing a similar approach across projects, we will perform BIA to frame affordability to the VHA.⁷³ We will calculate the budget impacts of the clinical programs and compare them to each program's value. Value will be defined in light of all of the evaluation evidence. For example, value may be framed as total budget impact per unit gain in patient function or as total budget impact compared to the clinical team's narrative on how a program benefited patients. We will also consider framing budgetary impact against different domains, such as total costs by site or costs per Veteran participant. The clinical program leads will work with the implementation core to develop appropriate comparisons.

For the BIA we will consider three cost categories: (1) program-related implementation costs; (2) implementation strategy costs; and (3) resource utilization costs. We will not consider the fixed labor costs of implementation planning (e.g. stakeholder committee time) because these are one-time costs that would not occur if the clinical programs were implemented nationally. First, for **program-related costs**, we will measure personnel time and labor costs associated with preparing for and delivering the clinical programs using micro-costing. Clinical program trainer time and clinical delivery team time (including donated FTE) will be collected through personnel time logs and periodic time studies. Personnel time will be valued using VA Human Resources salary data. In addition to labor costs, we will consider program-related capital costs such as purchased durable equipment (e.g., walkers, measuring wheels, stop watches and portable pulse oximeters). Second, we will track **implementation strategy costs**, which includes REP and CONNECT training time, training materials, and site-visit travel. Travel costs will be measured using accepted per diem reimbursement, and the cost of personnel time will be measured as described above. Third, for **resource utilization costs** we will examine patient-level utilization pre-and post-clinical program by treatment and control subjects, to understand marginal costs/savings associated with the clinical programs.

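### The iHI-FIVES primary analysis does not pre-specify the Veteran's own earlier days not at home as a covariate, a cheap precision gain of uncertain size

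*Combined protocol and SAP*

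**What the plan says.** Under PROGRAM-SPECIFIC METHODS: iHI-FIVES, the primary outcome is reduced by days in the emergency department, an inpatient setting or a post-acute facility. All are counted from administrative and VA/CMS Repository records. Key covariates gives the patient-level list as "factors known to assess independence including age, race, ethnicity, marital status, service connection, urban/rural status, NOSOS score from year prior to start date". The list is introduced as examples, so other variables are not excluded.

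Analyses, Aim 2b, sets out the primary analysis only as a choice of distribution (Poisson, negative binomial, their zero-inflated forms, or a two-part model). The stated reason is that "it may have an excess of zeros and larger variance than what is to be expected from either a Poisson or Negative Binomial process". No covariate is named there. The one sentence on adjustment, "Adjustments for patient characteristics and a random effect for VAMC site may also be added", is optional and closes the paragraph on the caregiver outcomes.

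Sample size estimate takes as inputs that "8 is the baseline mean number of days not at home over 6 months" and a "2-day reduction in days not at home over 6 months", and claims for 400 Veterans "at least 80% power to detect a mean reduction of 2 days not home assuming variance equal to the mean (Poisson distribution".

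For costs only, Budget impact analyses says "we will examine patient-level utilization pre-and post-clinical program by treatment and control subjects".

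**The concern.** A patient's earlier value of a utilisation outcome is a natural candidate for adjustment. Here it could be counted from the same sources, under the same rules, with no patient contact. The plan names demographics and a prior-year risk score but not this variable.

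What is at stake is the width of the interval around the 2-day effect. Aim 2b allows for variance well above Poisson. To the extent that this variance reflects differences between Veterans that were already visible before referral, the earlier count would absorb part of it. Pre-specification matters because there are only eight sites, two per step. Chance differences in prior utilisation between exposed and unexposed site-periods are plausible, and a covariate added after the outcomes are seen is open to challenge.

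**Working it through.** **Inputs from the documents.** Sample size estimate gives 8 VAMCs, five 6-month intervals, baseline mean 8 days, effect 2 days, CV 0.3 to 0.5, alpha 0.05, and variance equal to the mean. The iHI-FIVES study timeline gives 4 steps of 2 VAMCs. The minimum of 400 Veterans is 400/(8 × 5) = 10 per VAMC-period. The anticipated 15,000 to 18,000 is 375 to 450 per VAMC-period; 400 is used below.

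**Assumed, because the documents give no figure.** A two-sided test; an SD of days not at home of 16 to 30; and rho, the partial correlation of earlier with later days given the covariates already used, of 0.2 to 0.5.

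**Formula.** Hussey-Hughes with I = 8, T = 5, s² = residual variance / n per VAMC-period, and τ = CV × 8. The step pattern gives U = 20, W = 120 and V = 60, so

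Var(θ) = I·s²·(s² + T·τ²) / [(I·U − W)·s² + (U² + I·T·U − T·W − I·V)·τ²] = 8·s²·(s² + 5τ²) / (40·s² + 120·τ²).

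Power = Φ(2/SE − 1.96). Adjustment multiplies the residual variance by (1 − rho²).

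**Step 1: the plan's own figure.** With variance 8, n = 10 and CV 0.3, s² = 0.8 and τ² = 5.76. Var = 6.4 × 29.6 / (32 + 691.2) = 0.262, SE = 0.512, and power = Φ(1.95) = 97.4% (97.3% at CV 0.5). The claim of at least 80% holds with room to spare. If variance really equals a common mean, an earlier count has nothing to explain.

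**Step 2: anticipated sample, larger variance.** With SD 25, n = 400 and CV 0.3, s² = 625/400 = 1.5625. Var = 12.5 × 30.3625 / (62.5 + 691.2) = 0.504, SE = 0.710, and power = 80.5%. With rho 0.5, s² = 1.172, SE = 0.617, and power = 90.0%. Power for the range of assumptions:

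| SD (days) | Unadjusted | rho 0.2 | rho 0.3 | rho 0.5 |
|---|---|---|---|---|
| 16 | 99.2% | 99.4% | 99.5% | 99.9% |
| 20 | 93.9% | 94.7% | 95.6% | 98.1% |
| 25 | 80.5% | 82.0% | 83.9% | 90.0% |
| 30 | 65.7% | 67.4% | 69.6% | 77.5% |

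At CV 0.5 the SD 25 row is 79.6%, 81.2%, 83.2% and 89.5%. Expressed as sample size, 1/(1 − rho²) − 1 gives about 4%, 10% and 33% more Veterans.

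**Step 3: site-by-period variation.** A patient covariate does not remove random variation between periods within a site. With an assumed site-by-period SD of 0.8 days added to the SD 25, CV 0.3 case, power is 66.6% unadjusted, 67.8% at rho 0.2, 69.3% at rho 0.3 and 74.7% at rho 0.5.

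**Step 4: the minimum sample.** At n = 10 the gain is sizeable only in a narrow band. At variance 16 (SD 4), power goes from 79.6% to 83.1% (rho 0.3) or 89.3% (rho 0.5). At SD 20 it goes from 9.4% to 11.0% even with rho 0.5, so adjustment would settle nothing there.

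**The case against.** - **The omission can be overstated.** A reader might infer that the analysis excludes the earlier count. It does not. The covariate list is open, and it already holds a prior-year score (NOSOS) that may carry part of the same information. What stands is that the earlier count is not pre-specified.
- **The premise is not documented.** A reader might infer that the excess variance is mainly stable differences between Veterans. Aim 2b says only that excess zeros and larger variance may occur. The iHI-FIVES rationale describes referral as a crisis point, so days before it may predict later days less well than in a stable population. Rho is therefore unknown, and gains quoted at 0.5 alone would be favourable. This objection stands, which is why a range is shown.
- **The approximation is linear.** The (1 − rho²) factor does not carry over directly to zero-inflated or two-part models. The percentages are a guide to size only.
- **The data are not already in hand.** The budget impact analysis compares costs around the programme and does not define a pre-referral count. The nursing-home residence rule sets no look-back window. The sources are the same, but one further extraction is needed.
- **The look-back is not always clean.** Sites keep offering the programme after go-live and may recruit caregivers outside the referral route. Of the 20 exposed site-periods, all except each site's first (20 − 8 = 12) can include Veterans whose look-back falls partly or wholly after go-live. This stands as a cost of the change.

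**Conclusion.** The point holds as an efficiency improvement at the level of something to consider. The earlier count of days not at home is not pre-specified for the iHI-FIVES primary analysis, and it can be built from the sources used for the outcome. Any non-zero partial correlation would narrow the interval. At the anticipated sample size with SD 25 and CV 0.3, the gain is 1.5, 3.4 or 9.5 points of power at rho 0.2, 0.3 or 0.5. It is smaller with site-by-period variation and negligible at SD 16 or less. SD and rho are both assumptions.

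The documents do not support reading this as a bias or as a failure of the stated power calculation. On the plan's own Poisson inputs, power is 97% without the covariate.

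**What to change.** First reconcile day 0. The Patient Outcome paragraph and Aim 2b count from the data pull, while Definition of the Primary Outcome starts the outcome period at the mid-point of each 6-month block.

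Then, in Key covariates and in the Aim 2b primary model, pre-specify days not at home in the 180 days before the Veteran's first qualifying referral. Use the same emergency department, inpatient and post-acute rules, and enter it as any/none plus log(1 + days), alongside NOSOS. End the look-back at referral rather than at the data pull, because the programme is offered after referral and a later cut-off could adjust away part of its effect. Report the programme effect as a model-standardised mean difference in days, so that it stays on the 2-day scale of the sample size whichever distribution is chosen. Give the result without this covariate as a sensitivity analysis.

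The cost is SAP wording and one look-back extraction, with no new patients or contacts. The downsides to state are a missing-record category for incomplete earlier VA/CMS data, an older baseline for Veterans who appear in repeated pulls, and look-backs that for later referrals fall partly or wholly after site go-live.

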Participating Sites. With our partners in the VA CSP, we will recruit sites in blocks of 4 based on our stratified stepped wedge design for a total of 8 volunteer VAMC sites for iHI-FIVES implementation (see letter of support from National Director [name]). To ensure sites are similar enough to compare between arms, sites are required to implement at least two rounds of iHI-FIVES training every six months. The full standard curriculum of HI-FIVES (e.g. if the sites choose all core and optional items to deliver) is 12 weeks in duration; delivering only the core curriculum would take four weeks of group classes. We anticipate some potential volunteer sites will be high functioning and primed for more successful implementation at baseline (i.e., based on their past performance in training and other performance metrics). Thus, we will work with our operational partners to review the volunteer pool to obtain diversity of sites based on a priori ease of implementing a new clinical program

(e.g. high performing, late adopter). We will explore with the implementation core the need to stratify by 'baseline site performance'. Eligible sites will need to have at least 50 recent referrals to Veteran directed care, home-based primary care, homemaker home health aide services, adult day health care, or respite care in a 3 or 6-month period to provide enough patient and caregiver volume to offer training (and for evaluation purposes). We are designating 3 or 6 months because, although we prefer a shorter window of 3 months, feasibility of site volume may lead us to use a 6-month period. Thus, we will assess the referrals on each interested site to make sure there is sufficient volume. We will conduct site visits at all participating sites prior to implementation to obtain additional important contextual information and baseline data for analysis.

Please see letter from [name], National Director, Caregiver Support Program (10P4C), providing certification of non-research operations activities status (Appendix B).

STUDY DESIGN

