Penetration will be measured using caregiver-level and provider-level measures at each site. *Caregiver-level*. We will measure penetration of the program at each site by assessing the number of caregivers "reached" by iHI-FIVES in a 6-month interval out of the total number of caregivers "eligible" during the same interval. *Provider-level*. Penetration at the provider-level will be measured as the number of providers who refer caregivers to participate in iHI-FIVES in a 6-month interval out of the total providers involved in caregiver support. *Site level*. Penetration at the site-level will be measured as the number of caregivers registered into the Caregiver Application Tracker (CAT) out of the number registered in the prior 6-months.

Fidelity will be measured as follows: 1) the number of 6-month intervals in post-implementation in which a site delivered at least two rounds of iHI-FIVES trainings out of the total number of 6-month intervals in post-implementation; 2) the number of rounds of training in which the full iHI-FIVES core curriculum topics were covered out of the total number of rounds of training offered.

These data will be obtained from review of electronic medical records via VistaWeb or Joint Legacy Viewer JLV, CDW data pull of health factor data, training records and attendance logs for each site, POC-reported data on instructors involved, and caregiver participant interviews.

Patient Outcome: Our primary individual-level outcome for iHI-FIVES is a patient-level outcome. Veteran **independence** (i.e., days spent alive and at home over the 6-month outcome period). This will be calculated as 180 days after the data pull date for that specific 6-month interval minus the total number of days **in an Emergency Department (ED) setting, an inpatient setting, or in a post-acute facility in the 6 months after the study start date (e.g., 6 months post-data pull).**

Caregiver Outcomes: Function. Our primary caregiver-level outcome of interest is **function** which includes depressive symptoms, as well as subjective **burden** (or the level of stress felt by CGs), and global **satisfaction** with VA health care quality measure as perceived by the caregiver. Caregiver outcome data will be obtained from surveys.

Patient data: Definition of the Primary Outcome

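### iHI-FIVES lets a Veteran enter at several data pulls but writes no Veteran-level term; if pulls are quarterly, the 180-day windows overlap and the primary standard error is too small

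*Combined protocol and SAP*

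**What the plan says.** All references are to the combined protocol and SAP.

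- **Pull schedule** (iHI-FIVES, Sample of Patients): the pull is repeated at a uniform time "of each 3 or 6-month interval for the duration of the 30-month study". The interval is not fixed.
- **Eligibility** (same section): "a consult or referral in the past 3 or 6-months from the date of the data pull" to one of five listed services. The one exclusion is "Consult or referral to hospice care". Earlier inclusion is not an exclusion.
- **Reason for the open choice** (iHI-FIVES, Participating Sites): "although we prefer a shorter window of 3 months, feasibility of site volume may lead us to use a 6-month period". This sentence concerns the referral window.
- **Outcome window**: Aim 2b puts day 0 at the automated pull, and "the maximum total possible number of days at home will be 180 for all patients". The Patient Outcome paragraph says "This will be calculated as 180 days after the data pull date for that specific 6-month interval". Definition of the Primary Outcome instead starts the window at the middle of each 6-month block and runs it forward 6 months.
- **Model** (Aim 2b): random-effect models "which account for the correlation of patients within the same VAMC". The equation has a VAMC effect, a period effect and an intervention effect. Patient characteristics and a further site effect are optional. No Veteran effect appears.
- **Double-counting checks** (Definition of the Primary Outcome): these separate ED, inpatient and post-acute days from each other. They do not deal with a second record for the same Veteran.
- **Contrast**: the QUERI ADIL analysis of the STRIDE data states that its models will handle several hospitalizations per patient. iHI-FIVES has no matching statement.

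**The concern.** A Veteran referred more than once to these services over 30 months can supply several records. A model with only a VAMC effect treats those records as different people.

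If pulls are 3 months apart and each opens a 180-day window, consecutive windows share 180 - 90 = 90 days. A hospital stay in the shared part then adds to two outcomes. At a site where one pull falls 3 months before crossover and the next at crossover, the shared days all follow the switch, so one admission can enter as both a control and an intervention outcome.

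At stake is the calibration of the test and confidence interval for the iHI-FIVES primary outcome. There is also a risk that two analysts following the text would build different datasets.

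**Working it through.** **1. The plan's power figure.** Inputs from Sample size estimate: 8 VAMCs, five 6-month intervals, baseline mean 8 days, reduction of 2 days, variance equal to the mean (8), CV 0.3 to 0.5, alpha 0.05 (taken as two-sided), 400 Veterans. I use 10 per VAMC-interval because 8 x 5 x 10 = 400; the 20 per interval also printed there would give 800. I assume two VAMCs cross at each of four steps.

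Hussey-Hughes variance, with s2 = 8/10 = 0.8 and tau = CV x 8:

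Var = I s2 (s2 + T tau2) / [(IU - W) s2 + (U2 + ITU - TW - IV) tau2], with I = 8, T = 5, U = 20, W = 120, V = 60 (tau2 and U2 are squares).

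- CV 0.3 (tau2 = 5.76): 189.44 / (32 + 691.2) = 0.262; SE 0.512; power = Phi(2/0.512 - 1.96) = 97.4%.
- CV 0.5 (tau2 = 16): 517.12 / (32 + 1920) = 0.265; SE 0.515; power 97.3%.

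The stated floor of 80% is met.

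**2. Effect of repeat Veterans on the SE.** The estimator is a weighted sum of VAMC-by-pull means. With large cells the weights are proportional to the treatment indicator centred by row and column. For five periods, one VAMC per step:

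| Crosses at | P1 | P2 | P3 | P4 | P5 |
|---|---|---|---|---|---|
| P2 | -0.30 | 0.45 | 0.20 | -0.05 | -0.30 |
| P3 | -0.10 | -0.35 | 0.40 | 0.15 | -0.10 |
| P4 | 0.10 | -0.15 | -0.40 | 0.35 | 0.10 |
| P5 | 0.30 | 0.05 | -0.20 | -0.45 | 0.30 |

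Let r be the share of a pull recurring at the next pull and rho the correlation of the two outcomes. Then

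(true SE / model SE)^2 = 1 + 2 x sum over lags k of (share x correlation at lag k) x c_k,

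where c_k is the sum of products of weights k pulls apart, divided by the sum of squared weights. The VAMC variance drops out because each row sums to zero.

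*Half-yearly pulls.* Sum of squares 1.5; lag-1 products -0.20; lag-2 products -0.55. So c1 = -0.133 and c2 = -0.367; likewise c3 = -0.133 and c4 = +0.133.

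*Quarterly pulls.* Each weight appears twice, so the sum of squares is 3.0. Lag-1 products are 1.5 (same block) - 0.20 (adjacent blocks) = 1.3, so c1 = 0.433.

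**3. Assumed inputs.** The documents give neither r nor rho. I take r = 10% to 50%. For half-overlapping windows I take rho = 0.5 (shared days only) to 0.7; for abutting windows, 0 to 0.3.

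| Reading | r | rho | (ratio)^2 | SE ratio | Size of 5% test |
|---|---|---|---|---|---|
| Quarterly | 0.10 | 0.5 | 1 + 2(0.05)(0.433) = 1.043 | 1.02 | 5.5% |
| Quarterly | 0.50 | 0.5 | 1 + 2(0.25)(0.433) = 1.217 | 1.10 | 7.6% |
| Quarterly | 0.50 | 0.7 | 1 + 2(0.35)(0.433) = 1.303 | 1.14 | 8.6% |
| 6-monthly | any | 0 | 1 | 1.00 | 5.0% |
| 6-monthly | 0.50 | 0.3 | 1 + 0.6(-0.0667 - 0.0917 - 0.0167 + 0.0083) = 0.90 | 0.95 | 3.9% |

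Size is 2 x (1 - Phi(1.96/ratio)). The 6-monthly rows let repeats persist (share r^k at lag k). The quarterly rows count repeats at the next pull only; letting them persist lowers the top ratio from 1.14 to about 1.11.

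**4. Power at the worst quarterly row, n = 400.** Phi(2/(0.515 x 1.14) - 1.96) = Phi(1.45), about 93%. This is still above 80%.

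**The case against.** The strongest reply is that the outcome text points to one window per 6-month block. The Patient Outcome paragraph ties the pull date to a specific 6-month interval, Definition of the Primary Outcome gives one period per block, and the design has five 6-month intervals. On that reading windows abut and no hospital day counts twice. The 3-or-6-month wording may concern only the referral look-back, which is what Participating Sites discusses. This stands as a likely reading. It is not the only one, because Sample of Patients applies the same choice to the pull itself and Aim 2b starts each window at the pull.

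Second, the model equation sits in a paragraph that opens with caregivers and gives n = 320, while the primary-outcome paragraph discusses only the distribution. That is fair. But the equation's paragraph covers patient-level and count outcomes, and no other correlation structure is written for the primary outcome.

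Three stronger inferences are tempting and not supported:

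- *That the primary error bars are certainly too narrow, by up to 21% with a test size of about 10%.* That needs quarterly pulls, 75% repeats, rho 0.7 and no later repeats.
- *That one referral will qualify a Veteran twice.* That needs a 6-month look-back combined with 3-month pulls. The text neither describes nor rules out this mix; with steady referrals it would give about 50% repeats. With matched intervals, each re-entry needs a new referral.
- *That the 15,000-18,000 figure counts records.* The text says Veteran patients. The wording fits one record per person but sets no rule.

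**Conclusion.** The concern holds in conditional form. The plan allows re-entry, states no one-record rule, and writes no Veteran-level term for the iHI-FIVES primary analysis. The consequence depends on the pull interval:

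- **Quarterly pulls with day 0 at the pull:** about 90 of 180 days are shared, the true SE is about 1.02-1.14 times the model SE, and test size is about 5.5-8.6%.
- **One window per 6-month block:** no days are shared, the SE ratio is about 0.95-1.00, and the test is correct to modestly conservative.

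These figures rest on an assumed 10-50% repeats, the assumed correlations, equal cell sizes and a linear mixed model rather than the skewed count models the plan lists. They indicate direction and order of size. The stated power of at least 80% is not in doubt under the plan's own Poisson variance. This is more than a missing detail, because the open choice decides the direction of the error and a better-specified analysis is available from the same data.

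**What to change.** 1. Align Sample of Patients, Patient Outcome, Definition of the Primary Outcome and Aim 2b on one 6-month pull at every site and one window start.
2. Keep one record per Veteran per interval. If quarterly pulls are needed for volume, allow re-entry only after 180 days, so that windows cannot overlap.
3. Add to the primary model a Veteran-level random intercept nested in VAMC, or a covariance that allows for repeated Veterans within VAMC, whichever outcome distribution is chosen.
4. Report the number of Veterans and the number of records separately, by period.

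The cost is revised wording in the SAP and the data-pull specification, the loss of some duplicate records, and a slightly more complex model. No new data are needed.
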